Formative usability testing (i.e. Stage 1): according to BS-EN 62366, Iterative testing performed throughout the design and development to explore user interface strengths and weaknesses

Summative usability testing (i.e. Stage 2): according to BS-EN 62366, Final testing stage at the end of design and development to obtain objective evidence to validate user interface

4. Background

A well-fitting and comfortable prosthetic socket is a priority for patients as it is the determining factor in enabling mobility and participation in society^{1,2}. It is also a clinical priority, with:

NHS

North Bristol

- Increasing demand for prosthetics, with 7,000 amputations/year by NHS England³, which is growing due to ageing populations, rising diabetes prevalence, and the COVID19 backlog
- NHS cost burden of £60M and growing²
- Need to support prosthetists to achieve optimal socket fit, faster, with fewer device rejections

The socket represents the interface between the residual limb and prosthetic componentry. However advanced the componentry, if the socket interface lacks the necessary balance of firm limb-device coupling and comfort, the limb's function will be impaired to the extent that the person may choose not to use the prosthetic limb. This situation is indeed common: rejection rates are $31\%^4$. Sockets are designed by a prosthetist, in a process that aims to optimise comfort, stability and mobility for the prosthesis user. In addition, socket fit is dependent on multifactorial patient differences including limb shape, soft tissue stiffness, regional tolerance to load and comorbidities. Sockets are not a 1:1 match of limb shape; instead, the prosthetist makes modifications, or "rectifications," to the baseline limb shape. This is intended to load pressure-tolerant limb regions, and off-load pressure-sensitive sites, to produce a secure and comfortable interface between patient and prosthesis. Rectification is a highly complex, skill- and experience-based process, yet there is little objective guidance or evidence to support prosthetists who require years of training and experience to hone their skills. This complexity leads to multiple iterative re-fittings, with an average of 9 visits to prosthetists in the first postoperative year⁵. Whilst some adjustment and re-fitting is inevitable as the residual limb stabilises in shape and volume, the clinical community is calling for tools to support them in taking a more evidence-based approach to the fitting process, to tackle these service inefficiencies and their socioeconomic impacts.

Since 2014, understanding how best-practice in engineering design can support prosthetic socket fitting has been a key focus of University of Southampton researchers. This research has resulted in the spin out of a company (Radii Devices Ltd.) and the development of technology to meet the patient and clinic need, guided by input from prosthetics service providers including Opcare (Ability Matters Group Ltd.), and patients. This study is assessing the usability of the developed software, Adaptive Templates Fitting System (ATFS), incorporating the technology. These Adaptive Templates use existing socket fitting data, which is analysed to link rectification approaches to particular patient characteristics. The data includes socket designs, limb shapes, and outcome measures from previous socket fittings in the NHS. The ATFS is derived from these datasets in two ways:

1) Extracting features from the complex 3D shapes of the residual limb and prosthetic socket, used for past patients. These may include individual rectifications, and clinically relevant residual limb features, such as the length, and how bulbous or conical their limb is.

2) Making a recommendation to a prosthetist for socket rectifications, using a probabilistic approach which considers the likelihood of particular socket design strategy working for a new patient's characteristics.

Unlocking the potential of data to support fitting will assist more efficient learning and design, potentially leading to:

- Reducing time to fit (fewer iterations, reduced waiting time and, eventually, reduced appointment backlog)
- Reducing rejection rates (improved comfort and functional stability)

NHS

North Bristol

• Improving patient outcomes, participation and quality of life (reduced incidence of soft tissue problems, from irritation and sores to major injuries such as pressure ulcers; reduced incidence and progression of comorbidities, including sequelae of immobility, obesity, vascular disease and mental health impacts)

The developed technology, using computational geometry, data science and biomechanical engineering expertise to extract meaningful data about the rectification process has been applied to below-knee prosthetic socket design data provided by Opcare. This data helped form an initial demonstration of the feasibility of linking rectification approaches to particular patient characteristics and objectively analysing personalised design approaches by expert prosthetists⁶.

A preceding related study (IRAS ID: 313408, EGRO NO: 76033, REC REF: 22/YH/0215, 01/02/23 – 30/11/23) is being conducted by the same team to compare sockets designed by a clinician to sockets designed by the underlying technology, to explore the feasibility of the proposed new approach. The aims of the study are to understand the strengths and limitations of the technology and fine tune its recommendations. These findings are being used in parallel to develop the ATFS; a full system usable by prosthetists in-clinic to support their socket design process.

The objective of this proposed new study is to evaluate the in-clinic usability of the ATFS, whose development was informed by the preceding feasibility study.

The output of the ATFS is a human-readable instruction set of the recommended rectifications to apply to the residual limb shape to create the socket in their relevant units (mm or %), which takes seconds to produce after upload of the residual limb scan. From here, the prosthetist can accept or edit each recommendation according to their clinical assessment. Therefore, the system is a tool to support the prosthetist based upon historical best-practice.

Following the creation of the instruction set, the socket is created by applying these instructions to modify the captured shape of the residual limb. This process is achieved either digitally with CAD software, which are not considered medical devices in their standalone form, or even manually through modification of a plaster model.

The various use of the ATFS within the socket design process is outlined in the diagram below. The optimal use case, and the one which will be tested in this study, is for the CAD tools to be automatically populated by the template, once approved by the clinician. This case is only possible when using the Radii system due to the integration between the systems.

Alternatively, because the output of the adaptive template is a human-readable instruction set, the user could apply the recommendations through another medium, such as a 3rd party CAD system or even through modification of a plaster model. However, this approach would introduce additional time taken and steps within the process.

NHS Cambridge **University Hospitals**

NHS

The figure below illustrates the separation between CAD tools and the Adaptive Templates Fitting System. This system design is critical to ensure that the clinician is always responsible for the final socket design and can edit the adaptable templates as they see fit according to their expertise.

283-04A-04_(XF)_Study Protocol

HRA REC REF: 24/LO/0126 7 IRAS ID: 317901 ERGO NO: 81419

CONFIDENTIAL THIS DOCUMENT IS PROPRIETARY INFORMATION AND IS NOT TO BE REPRODUCED OR DISCLOSED WITHOUT PRIOR WRITTEN APPROVAL.

NHS

North Bristol

5. Research objective and tasks

4.1 Research Objective

Following the preceding study (IRAS ID: 313408, EGRO NO: 76033, REC REF: 22/YH/0215, 01/02/23 – 30/11/23), the objective of this study is to evaluate the clinical usability, in terms of safety and performance, of the Adaptive Templates Fitting System that combines Adaptive Templates technology with the experience and expertise of the clinician to provide optimal socket design support. It is important for this clinical investigation to verify the clinical safety and performance of the ATFS to comply with Section 1 of Annex I of the Medical Devices Directive; demonstrating when used for its intended purpose (support of socket design by prosthetists) the safety of patients (those receiving the designed sockets) will not be compromised.

The study will be carried out in two stages contextualised with longitudinal qualitative research, according to study design definitions from BS-EN 62366:

Stage One will explore the strengths and limitations of the in-clinic usability of the ATFS to inform its further development, reducing as far as possible the risk of use error due to user interface, and;

Stage Two will assess the in-clinic usability of the updated ATFS. This clinical investigation will verify the safety and efficiency of its in-clinic use by capturing:

- socket comfort scores of sockets designed using the ATFS to demonstrate non-inferiority compared to the current process (without the support of the ATFS) and socket comfort scores > 7, the NHS key performance indicator; and
- time taken for initial rectification and socket design using the ATFS compared to with the current process.

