6.2 Population size

Group A – Prosthetists

Prosthetists across the three NHS sites (up to 17 in total) will be recruited in the participating prosthetics centres, allowing several prosthetists' usability experiences to be captured. For Stage One (the iterative usability testing) BS-EN 62366 suggests that a sample size of 5-8 participants is sufficient. BS EN 62366 illustrates in Annex K that using small sample sizes identifies usability defects and reduces the required clinical resource.

A sample size of 15 participants is suggested according to BS-EN 62366 for the summative usability testing (Stage Two). This sample size gives a probability of capturing at least one occurrence of a usability defect of 91% (IEC/TR 62366-2:2016). A power analysis to determine sample size has not been carried out as BS EN 62366 discourages use of power analysis to determine sample size for usability studies.

A sample size of 17 was determined taking into account BS-EN 62366, the number of prosthetists at each of the NHS sites, allowing for 10% withdrawals, and matching similar published studies exploring clinician perspectives of socket fit¹⁰.

Group B – Adults with limb loss

A sample of convenience of up to 46 adults with transtibial limb loss will be recruited across the three participating prosthetics centres for this study. This sample size was determined by considering the number of usability study iterations that may take place, both patient and prosthetist withdrawals, and demonstration of the clinical usability within Stage Two.

Sample size was determined for the two stages as follows:

Stage One:

For each participating prosthetist in Stage One, one patient participant will be recruited per usability iteration. 5-8 prosthetists will participate in each usability testing iteration. Allowing for withdrawal

283-04A-04_(XF)_Study Protocol IRAS ID: 317901 ERGO NO: 81419 HRA REC REF: 24/LO/0126 10

CONFIDENTIAL THIS DOCUMENT IS PROPRIETARY INFORMATION AND IS NOT TO BE REPRODUCED OR DISCLOSED WITHOUT PRIOR WRITTEN APPROVAL.

North Bristol NHS Trust

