and for three iterations, a maximum of 27 patient participants would need to be recruited. Less participants may be recruited if fewer usability iterations are required in Stage One as determined by the technology development process (e.g., feature freeze), and the participating clinicians being comfortable to use the ATFS throughout the full socket design process independently without resorting to their current socket design process (i.e. no further observation or detection of a usability problem).

Stage Two:

A sample size of 19 will be recruited for Stage Two. This sample size was determined using a noninferiority result for a crossover group trial with normal socket comfort score data. We determined an appropriate sample size of 19 for this group (power: 0.9, significance level: 0.025, Mean Difference: 0, non-inferiority limit: 1.21, population Socket Comfort Score standard deviation: 0.998). This was using the NIHR SampSize web tool with the non-inferiority limit obtained from Hafner et al¹¹ and population standard deviation obtained from the ATFS training dataset¹² which is an extension to the population presented in Dickinson et al⁶. An addition of 10% was added accepting the uncertainty around the employed data.

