As per normal care, once the socket has been made the prosthetist will carry out a fitting appointment for the patient, taking and recording standard outcome measures (e.g. socket comfort score, Key Performance Indicators (KPIs) for their clinic). They will discuss the socket fit with the patient and make minor or major socket adjustments as required, using the ATFS software where digital adjustments are needed, leading to delivering the definitive socket for the patient. The study researcher will be on-call to help where required with use of the ATFS. The socket comfort score will be collected from the prosthetist by a study researcher.

The study researcher will arrange to conduct a 30-minute semi-structured interview with the prosthetist after delivery of the definitive socket to the patient, about their experience creating a socket with the aid of the ATFS. Physical adjustments carried out on the socket during fitting appointments will also be captured during the interview. The prosthetist will have the choice of an in-person, virtual (via MS Teams video call software), or telephone interview. The interview will be arranged flexibly around the prosthetist's schedule.

Training materials on using the ATFS will also be evaluated through the semi-structured interview.

For the iterative development of the software being carried out during this first stage, the prosthetist may be asked to carry out stage one of the study at least once more. Software updates will be pushed throughout Stage One while developing the ATFS and researchers will be present to support ATFS use and provide training as required. The Stage One endpoint and number of usability iterations required in Stage One will be determined by the technology development process (e.g., feature freeze), and the participating clinicians being comfortable to use the ATFS throughout the full socket design process independently without resorting to current socket design process (i.e. no further observation or detection of a usability problem with final ATFS version reached and ready for summative testing).

283-04A-04 (XF) Study Protocol IRAS ID: 317901 HRA REC REF: 24/LO/0126 12 ERGO NO: 81419

See Group B – Stage 1 semi-structured interview format in the Appendices of this document in Section 16.1.

Stage One Group A (participating prosthetists) Pathway Diagram:

Stage One (Formative) testing - 081222

283-04A-04_(XF)_Study Protocol

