6.5 Stage Two Procedure – Group A

Stage Two consists of Summative usability testing of the fully developed ATFS. Training will be provided if a participant interested in taking part in only Stage Two did not attend a Stage One training session.

NHS

North Bristol

(Please see prosthetists pathway diagram on Page 15)

Identical to Stage One except for the following changes:

- i. The prosthetist will use the ATFS independently while being recorded but without thinking aloud.
- ii. No changes will be made to the ATFS during this stage.
- iii. The study researcher will arrange to conduct a 30-minute semi-structured interview with the prosthetist after delivery of the definitive socket to the patient, about their experience independently creating a socket with the aid of the ATFS, plus their views on comparisons against their standard CAD/CAM design workflow.

The interviews will be arranged flexibly around the prosthetist's schedule.

See Group A – Stage 2 semi-structured interview schedule in the Appendices of this document in Section 16.1.

NHS Cambridge **University Hospitals**

NHS

Stage Two Group A (participating prosthetists) Diagram:

Stage Two (Summative) testing - 081222

CONFIDENTIAL THIS DOCUMENT IS PROPRIETARY INFORMATION AND IS NOT TO BE REPRODUCED OR DISCLOSED WITHOUT PRIOR WRITTEN APPROVAL

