6.8 End of Study Stage One end point

283-04A-04_(XF)_Study Protocol

IRAS ID: 317901 ERGO NO: 81419 HRA REC REF: 24/LO/0126 16

NHS North Bristol NHS Trust

Once the final ATFS version has been reached ready for summative testing. The number of iterations required in Stage One will be determined by the technology development process (e.g., feature freeze), and the participating clinicians being comfortable to use the ATFS throughout the full socket design process independently without resorting to their current socket design process (i.e., no further observation or detection of a usability problem).

Stage Two end point

Once the ATFS has been used to support the socket design for 19 participating patients across the three sites.

7. Data analysis

Continuous data (i.e. time taken for initial rectification and socket design using the ATFS) will be summarised using mean, standard deviation, median and 25th and 75th percentiles; categorical data (i.e. socket comfort scores) will be summarised using number of events and percentages. Completion rates of the data above will be tracked.

The qualitative data collected from audio recordings will be transcribed verbatim by a University of Southampton approved subcontractor, with whom the University has a written agreement of confidentiality. A second researcher will check a sample of data transcripts against the screen capture with audio and interview recordings for accuracy, and will interrogate the validity of the coding against the raw data. The verbal content of the interviews, and the verbal and observational data of the screen capture recordings will be analysed. The data will be fully anonymised to remove any identifying (i.e., names) and confidential information. Interview data for Stage 1 and 2 will be analysed separately using thematic analysis; a flexible approach will be applied to systematically group and identify meaning within the data^{13, 14}, and will be useful for the more in-depth discussions within the interviews. This analytical approach will consist of a series of steps including: familiarisation with the data, a combination of hand-coding and the QSR International NVivo 11 software (http://www.qsrinternational.com/what-is-nvivo), and searching, defining and reviewing themes.

8. Adverse events and Serious Adverse Events Reporting

NHS

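### Section 4.1 commits the study to demonstrating that patient safety is not compromised, but comfort score and design time do not bound harm and 19 patients on the frozen ATFS cannot exclude event rates below about 15%

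*Protocol*

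**What the plan says.** Protocol Section 4.1 ties the study to regulatory conformity. The investigation is to verify clinical safety and performance, demonstrating that when the ATFS is used as intended "the safety of patients (those receiving the designed sockets) will not be compromised".

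The same section says how this is to be done in Stage Two: "This clinical investigation will verify the safety and efficiency of its in-clinic use by capturing" two things. These are socket comfort scores (non-inferior to the current process and above 7) and the time taken for rectification and design. No event-rate criterion is listed.

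On exposure:
- Section 6.2: "A sample size of 19 will be recruited for Stage Two". The number comes from a non-inferiority calculation on comfort score.
- Section 6.8, Stage Two end point: "Once the ATFS has been used to support the socket design for 19 participating patients across the three sites".
- Section 6.5, on Stage Two: "No changes will be made to the ATFS during this stage".
- Section 6.4: "Software updates will be pushed throughout Stage One while developing the ATFS".
- Section 6.2, on Stage One: "a maximum of 27 patient participants would need to be recruited". Over both stages, "up to 46 adults with transtibial limb loss will be recruited".

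Section 8 leaves adverse events to be recorded by prosthetists within usual care, and plans a causality assessment for serious adverse events (SAEs) only. The protocol gives no expected or acceptable event rate. Under Section 6.6 every participant's socket is designed with the ATFS, so there is no usual-care group.

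**The concern.** The safety sentence in 4.1 is a conclusion that the study is meant to deliver. The design does not reach it, for three reasons.

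- **The named measures do not measure harm.** Section 4 mentions sores and pressure ulcers, and Section 8 gives an injurious fall as an example of an SAE. A non-inferior mean comfort score says nothing about how often these occur, and design time says less. As Section 6.6 describes it, comfort is scored at the fitting appointment, before the patient takes the socket home.
- **Exposure to the frozen version is small.** It is 19 patients, and harm played no part in choosing that number.
- **There is nothing to compare with.** Not being compromised is naturally read as no worse than usual care, and the protocol collects no usual-care event rate.

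At stake is a safety statement offered for regulatory conformity that is stronger than the data could support, however well the study runs.

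**Working it through.** **The plan's own figure.** Inputs from Section 6.2: power 0.9, significance level 0.025 (taken as one-sided), true difference 0, margin 1.21, SD 0.998, plus 10%.
- Normal approximation for a crossover: N = 2 × [0.998 × (1.960 + 1.282) / 1.21]² = 14.3, so 15.
- Noncentral t with standard error SD × √(2/N) and N − 2 degrees of freedom: the smallest N with power of at least 0.90 is 17 (power 0.910).
- Adding 10%: 17 × 1.1 = 18.7, so 19.

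The stated 19 is reproduced, for comfort score.

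**What zero events would show.** The protocol gives no confidence level for a safety statement, so both common conventions are shown. With no events in n patients, the exact binomial upper limit is 1 − 0.05^(1/n) (one-sided 95%) or 1 − 0.025^(1/n) (two-sided 95%).

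| Patients | One-sided 95% | Two-sided 95% |
|---|---|---|
| 19 (Stage Two, frozen ATFS) | 1 − 0.05^(1/19) = 14.6% | 1 − 0.025^(1/19) = 17.6% |
| 46 (27 + 19, both stages) | 1 − 0.05^(1/46) = 6.3% | 1 − 0.025^(1/46) = 7.7% |

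As a check, the rule of three gives 3/19 = 15.8%. The 46-patient row pools up to 27 patients whose sockets were designed while the software was still being updated, so it is supporting evidence only.

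**How often a clean result would be seen anyway.** The true rates here are illustrative and not from the protocol. P(no event in 19) = (1 − p)^19.
- p = 5%: 0.95^19 = 0.377, or 38%.
- p = 10%: 0.90^19 = 0.135, or 13.5%.

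No events in 19 would therefore be unremarkable at a true rate of 5% and uncommon, though far from excluded, at 10%.

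**For scale.** The number of event-free patients needed for a one-sided 95% upper limit of at most p is ln(0.05)/ln(1 − p), rounded up: 29 for 10% and 59 for 5%.

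**The case against.** The strongest reply is that the protocol never proposes to infer safety from an absence of events. It names comfort score and design time as its route, and Section 4.2 adds qualitative findings. This stands as a description. A reader might infer that the sponsor plans to count zero events in 19 and declare safety shown, but no section says so. The reply does not rescue the sentence, because the route that is stated bounds harm even less than an event count would.

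The clause can also be read as regulatory purpose language. A risk analysis, investigator's brochure and Clinical Investigation Plan are cited but not shown, so it cannot be said that conformity rests on these 19 patients alone. That limits what may be alleged. It does not change what this study can demonstrate, since no criterion in another document makes 0/19 exclude rates below about 15%.

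The prosthetist can edit every recommendation and remains responsible for the socket (Section 4), and the patient takes it home only once both are satisfied (Section 6.6). These are fair reasons to expect low risk, but they are not a demonstration by this study.

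Finally, any small device study leaves uncommon harms open, and interval reporting is often left to a statistical analysis plan. Both are true. The fault here is the strength of a conclusion written into the protocol.

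**Conclusion.** The point holds. Section 4.1 promises a demonstration that neither its named measures nor its exposure can provide. With no events, 19 patients on the frozen ATFS leave open a true rate of up to 14.6% (one-sided 95%) or 17.6% (two-sided 95%). All 46 leave 6.3% or 7.7%, with up to 27 on changing versions. A comparative claim has no usual-care rate behind it.

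The figures assume independent patients and complete ascertainment. Passive collection through usual care that missed events would make the true position less favourable than these limits.

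Two stronger readings go too far. A reader might infer that the sample size is wrong, but 19 is reproduced for its own comfort-score purpose. A reader might also infer that the ATFS is unsafe, but nothing in the protocol suggests it. The defect is the strength of the safety conclusion.

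**What to change.** **Section 4.1.** Limit the confirmatory statement to non-inferiority of socket comfort score. Restate the safety aim as describing the adverse events and SAEs observed.

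**Section 7.** Report, for Stage Two, the proportion of patients out of 19 with any adverse event and the proportion with any SAE (with its causality category), each with an exact two-sided 95% confidence interval. Give the pooled Stage One and Stage Two figures, out of up to 46, as supporting data. Any adverse event is the workable category, because Section 8 plans causality assessment only for SAEs. State that a zero count will be reported with its upper limit and confidence level (0/19: 17.6%, two-sided 95%), and not as safety demonstrated.

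**Cost.** A few sentences and no extra patients. The counts depend on the prosthetists' adverse event records reaching the study team. The E-CRF items in Section 16.2 include none for adverse events, so a field there or another stated route would be needed. The downside for the sponsor is a less favourable safety statement.

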4.2 Study Tasks

Stage One Tasks

- Iterative usability testing of the ATFS for supporting socket design, informing its further development.
- Iterative development of ATFS training materials.
- Design sockets for patients from NHS clinics, provided by Opcare, with the aid of the ATFS.
- Capture outcome measures (e.g., socket comfort scores).
- Explore prosthetists' views and experiences of using the ATFS in their current practice and pathways.
- Evaluate the strengths and weaknesses of the ATFS.
- Integrate findings from qualitative research to further understand experiences from the clinician's perspective to support the development of the ATFS.

North Bristol NHS Trust

Stage Two Tasks

- Usability testing of the final developed ATFS.
- Design sockets for patients from NHS clinics, provided by Opcare, with the aid of the ATFS.
- Capture outcome measures (e.g., socket comfort scores, time taken for initial rectification and socket design using the ATFS for comparison with the standard CAD/CAM socket design process).
- Explore prosthetists' views and experiences of independently using the ATFS in their current practice and pathways.
- Integrate findings from qualitative research to demonstrate safe and efficient clinical usability of the ATFS.

6. Methods and design

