This procedure matches normal care except that the socket will have been designed with the aid of the ATFS rather than the standard CAD/CAM socket design process for the clinic.

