16.2 Electronic Case Report Form (E-CRF) – Appendix B

283-04A-03 (XA) E-CASE REPORT FORM

Based on 283-04A-01 (XE) Radii Clinical Investigation Plan

Study title: Clinical usability evaluation of Adaptive Templates Fitting System for socket design

Details to be completed by a study researcher (one form per Group B participant):

* Required

* This form will record your name, please fill your name.

- 1. Group A Participant ID *
- 2. Group B Participant D *
- 3. Date Group B Screened *

				Ē
be				

4. Date Group B Consent Received *

1	-	

5. Date Group B on Study *

283-04A-04_(XF)_Study Protocol

IRAS ID: 317901 ERGO NO: 81419 HRA REC REF: 24/LO/0126 28

...

CONFIDENTIAL THIS DOCUMENT IS PROPRIETARY INFORMATION AND IS NOT TO BE REPRODUCED OR DISCLOSED WITHOUT PRIOR WRITTEN APPROVAL.

6.	Date	Group	В	Comp	eted	Study	1
----	------	-------	---	------	------	-------	---

- 7. Socket Comfort Score(s) (date and collect from Group A participant) *
- 8. Screen recording files for *

9. Screen recordings saved in master site file *

- 🔵 Yes
- 10. Time data for ATFS use saved in master site file *
 - 🔵 Yes
- 11. Semi-Structured interview audio recording saved in master site file *
 - Yes
- 12. Printed name of researcher *

283-04A-04_(XF)_Study Protocol

IRAS ID: 317901 ERGO NO: 81419 HRA REC REF: 24/LO/0126 29

CONFIDENTIAL THIS DOCUMENT IS PROPRIETARY INFORMATION AND IS NOT TO BE REPRODUCED OR DISCLOSED WITHOUT PRIOR WRITTEN APPROVAL.

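### The Stage Two efficiency aim compares ATFS design time with the current process, but the protocol records and summarises ATFS time only

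*Protocol*

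**What the plan says.** Section 4.1 (Research Objective) gives Stage Two two measures for verifying safety and efficiency. One is the socket comfort score. The other is "time taken for initial rectification and socket design using the ATFS compared to with the current process". The Stage Two tasks in Section 4.2 likewise list "time taken for initial rectification and socket design using the ATFS for comparison with the standard CAD/CAM socket design process".

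The sections that fix what is done and recorded are narrower:

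- **Section 6.5 (Stage Two procedure, prosthetists):** "The prosthetist will use the ATFS independently while being recorded but without thinking aloud". The contrast with usual practice comes from the interview, which asks for prosthetists' experience of the ATFS "plus their views on comparisons against their standard CAD/CAM design workflow".
- **Section 6.6 (patients):** usual care applies with one change, namely "the socket will have been designed with the aid of the ATFS rather than the standard CAD/CAM socket design process for the clinic".
- **Section 7 (Data analysis):** "Continuous data (i.e. time taken for initial rectification and socket design using the ATFS) will be summarised", by mean, SD, median and quartiles.
- **Section 10.3 (Stage Two per-participant activities):** the only design activity is use of the ATFS.
- **Section 16.2 (E-CRF), item 10:** "Time data for ATFS use saved in master site file". The form has no other time item.

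**The concern.** A comparison needs data on both sides, and the protocol provides for one. Time is the only quantitative measure that Section 4.1 assigns to efficiency. At the end of Stage Two the efficiency statement would therefore rest on an uncontrolled set of ATFS times placed beside prosthetists' impressions or a benchmark chosen afterwards.

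Such a comparison could err in either direction. Section 4 describes rectification as dependent on skill and experience, so design time can be expected to differ between prosthetists and between limbs, although the documents give no design times to show by how much. A benchmark from other staff, other patients or other start and stop events would mix those differences with the effect of the software. Section 4.1 presents the investigation as verifying the device's safety and performance for regulatory purposes, so an efficiency claim without a comparator would be open to challenge.

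**Working it through.** **1. The plan's own figure.** Section 6.2 sets Stage Two at 19 patients: crossover non-inferiority, power 0.90, significance level 0.025 (taken as one-sided), true difference 0, margin 1.21, SD 0.998, plus 10%.

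- Normal approximation: N = 2 × SD² × (z₀.₉₇₅ + z₀.₉₀)² / margin² = 2 × 0.998² × (1.960 + 1.282)² / 1.21² = 14.3, so 15.
- Noncentral t with N − 2 degrees of freedom: power 0.890 at N = 16 and 0.910 at N = 17, so N = 17.
- Adding 10%: 17 × 1.1 = 18.7, so 19.

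The 19 reproduces. It is sized on the comfort score alone. For time, the protocol states no SD, expected difference, margin or comparator value, so no power can be calculated for the time comparison as planned.

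**2. Where times could arise.**

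| Place in protocol | ATFS time | Current-process time |
|---|---|---|
| 4.1 and 4.2, objective and tasks | yes | promised as comparator |
| 6.5, recording of design | yes | no |
| 6.5, interview | – | opinion only |
| 6.6, sockets designed for participants | yes | none designed this way |
| 10.3, Stage Two schedule | yes | no |
| 7, planned summary | yes | no |
| 16.2, E-CRF | yes (item 10) | no |

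No outside source fills the right-hand column. Section 4 describes the existing fitting data as socket designs, limb shapes and outcome measures. It describes the preceding study as a comparison of sockets. Design times are mentioned for neither.

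**3. What the planned data can deliver.** For 19 ATFS times, the half-width of the 95% CI for the mean is t₀.₉₇₅,₁₈ × SD / √19 = 2.101 / 4.359 = 0.48 SD. With no comparator times, the difference and its interval cannot be computed.

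**4. What a paired comparator would deliver.** Assume one standard-process time and one ATFS time from each of 15 prosthetists, the Stage Two number that Section 6.2 takes from the usability standard. For a paired t-test at two-sided 5% and 80% power:

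- Normal approximation: (1.960 + 0.842) / √15 = 0.72 SD of the paired differences.
- Noncentral t: 0.778 SD.

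This cannot be put into minutes, because the documents give no SD for design time.

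**The case against.** The strongest reply is that Section 4.2 speaks only of ATFS time captured for comparison, which would fit a benchmark from outside the study. On that reading the defect is an unidentified comparator, not an impossible comparison. The E-CRF is a per-patient checklist and would not naturally hold times from non-study patients. The Clinical Investigation Plan, on which the E-CRF is based, is not at hand, nor is the Stage Two pathway diagram. The method of comparison could properly be left to a SAP. Finally, no hypothesis or decision rule is attached to time, and Section 4.2 also uses qualitative findings to support efficient usability.

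Some of this stands. The comparison is impossible from the data this protocol collects, and a sourced benchmark could in principle be used. If the Clinical Investigation Plan names one, the protocol should cite it. The silence of Section 7 on a comparison method is not a fault in itself. The 0.78 SD figure describes the proposed remedy and does not measure the flaw.

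The point survives. No benchmark is named in the protocol, and a SAP can choose an analysis but cannot create observations. Interview opinion is not a measurement of time.

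**Conclusion.** The concern holds. One of the two measures that Section 4.1 names for Stage Two cannot be delivered as written: 19 ATFS times are planned and no current-process times. The protocol contradicts itself between its objective and its data collection, and this should be resolved before Stage Two begins.

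The conclusion assumes that the protocol's text describes all the time data to be collected. The comfort-score sample size and the safety assessment do not depend on it. The figure of 0.78 SD rests on 15 prosthetists each supplying one pair of times. Section 6.2 allows up to 17 prosthetists, and averaging several designs per prosthetist would reduce the variance of each difference, so it is indicative only.

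**What to change.** **Preferred.**

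- Define the start and stop events for initial rectification and socket design, and apply them to both processes.
- For each participating prosthetist, obtain standard-CAD design times on that definition for a fixed number of recent routine transtibial designs. Take them from CAD session or file time-stamps, or log them in routine work during Stage Two.
- Add a field for these times. Because the E-CRF is completed once per patient, a short form per prosthetist is the better place.
- In Section 7, state a within-prosthetist comparison: the paired difference, or the ratio of geometric means, with a 95% CI. Acknowledge that the two sets of times come from different patients and may come from different periods.

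**Alternative.** If the CAD records hold no usable times and logging is not feasible, reword Sections 4.1 and 4.2 so that Stage Two describes the time taken using the ATFS, and drop the comparison.

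**Cost.** The preferred route needs one added data item and a log extraction or a few minutes' logging per prosthetist. The documents do not say whether usable time-stamps exist. Use of routine records from patients outside the study may need its own approval, since the consent described in Section 9 covers participants only. Historical timings may also be rougher than screen recordings. The alternative costs only a change of wording. Neither route alters patient care.
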